1.2 STUDY ENDPOINTS

1.2.1 Primary Efficacy Endpoint(s)

Primary efficacy endpoint in **Treatment Phase I** is to determine the effectiveness of FCM in improving RLS severity associated with IDA. Effectiveness will be evaluated by:

- IRLSS score change from baseline to Day 42 with comparison between FCM vs. Placebo.
- CGI-I at Day 42.

Primary efficacy endpoint in **Treatment Phase II** is to determine the effectiveness of an additional unblinded single FCM treatment in improving RLS severity in non-responders from Treatment Phase I. Effectiveness will be evaluated by:

- IRLSS score change from baseline (For Phase II the “baseline” is established on Day 42 of Phase I) compared to Day 42 of Treatment Phase II
- CGI-I at Day 42 in Treatment Phase II.

Primary efficacy endpoint in **Long-Term Extension Phase III** is to evaluate the duration of effect of FCM as defined as the number of weeks from the initial treatment without need for further treatment. Initial treatment is defined as Day 0 of Phase I for Responders in Phase I and Day 0 of Phase II for Responders in Phase II.

1.2.2 Secondary Efficacy Endpoint(s)

Treatment Phase I and Phase II:

- Change in IRLSS score from Baseline to Day 42. (Treatment Phase I and II)
- IRLSS score change from Baseline (For Phase II the “Baseline” is established on Day 42 of Phase I) compared to Day 42 of Treatment Phase II.
- CGI-I and PGI-I at each visit and percentage of subjects who are much or very much improved at Day 42. (Treatment Phase I and II)
- Change in sleep quality (MOS Sleep) from Baseline to Day 42. (Treatment Phase I and II)
- Estimate the proportion of treatment non-responders in Phase I who respond to FCM in Phase II for each randomized treatment group. (Phase II only)
- Change in substantia nigra iron index from Baseline to Day 42. The index will be determined using measures of MRI relaxation rate (R2*) or Quantitative Susceptibility Mapping (QSM). (Treatment Phase I and II)
- Change in iron index (R2* or QSM) for thalamus and motor cortex from Baseline to Day 42. (Treatment Phase I and II).

Treatment Phase III:

- Change in IRLSS total score from baseline to each scheduled visit.
- Number (and percentage) of subjects who remain in the study to Week 52.

1.2.3 Safety Endpoints

Safety endpoints include:

- Adverse events
- Laboratory assessments, including hematology (Hgb, Hct, RBC, WBC, MCV, MCH, MCHC, RDW, platelets, differential count), iron indices (serum iron, serum ferritin, and total iron binding capacity (TIBC), percentage serum transferrin saturation (TSAT)), clinical chemistry (sodium, potassium, chloride, BUN, creatinine, albumin, alkaline phosphatase, total bilirubin, gamma-GGT, AST, ALT, LDH, calcium, phosphorus, glucose, bicarbonate)
- Vital signs

1.3 SUMMARY OF THE STUDY DESIGN

1.3.1 General Study Design and Plan

This is a Phase II, randomized, placebo-controlled multi-center study to evaluate the efficacy and safety of Injectafer® (FCM Injection) for treatment of Restless Leg Syndrome (RLS) with iron-deficiency anemia (IDA).

FCM is a stable Type I polynuclear iron (III)-hydroxide carbohydrate complex developed as an intravenous (IV) iron replacement therapy for the treatment of IDA¹. All subjects who meet the inclusion requirements and no exclusion criteria will qualify to enter the screening phase. The study will include 3 treatment phases, i.e. Phase I (42 days), II (42 days) and III (46 weeks long-term extension), and will enroll 70 subjects to be randomized into Treatment Phase I.

In **Treatment Phase I**, all eligible subjects will be randomized in a 1:1 ratio to receive a blinded dose of either FCM 750 mg undiluted slow IV push at 100 mg/minute or a Placebo (15 ml of Normal Saline) IV push at 2 ml/minute on Days 0 and 7. At the end of treatment Phase I (i.e. Day 42), all subjects will be defined as either treatment responders or non-responders defined as:

Responder: IRLSS total score ≤ 10 , or IRLSS total score > 10 with a CGI-I score of much or very much improvement and the patient does not request further treatment for RLS.

Non-Responder: if neither of these above criteria are met.

In **Treatment Phase II**, Treatment Phase I Non-Responders who have met the necessary laboratory criteria (ferritin < 300 ng/mL and a TSAT $< 45\%$) will be consented for enrollment in Treatment Phase II. Day 0 of treatment Phase II will occur within 7 days of the completing Treatment Phase I Day 42 visit. These subjects will receive an unblinded 750 mg dose of FCM, treatments will be given as an undiluted slow IV push at 100 mg/minute on Days 0 and 7 of Phase II consequently. Treatment Phase I Non-Responders who do not meet the laboratory criteria for additional dosing will be discontinued from the study and treated for RLS as deemed appropriate by the referring physician. Subjects completing Treatment Phase II will be re-evaluated on Day 42 and defined as either a Responder or Non-Responder, using the same criteria described above. Treatment Phase II Non-Responders will be discontinued from the study after final assessments are complete.

In **Treatment Phase III**, responders from either Treatment Phase I or Treatment Phase II will continue through into this 46-week long-term extension phase of the study, and be monitored and assessed by phone for RLS symptoms (IRLSS and HRSQ) and adverse events on Weeks 15, 25, 34, 43 and 52 (final follow-up visit) from treatment Phase I Day 0. During Phase III, subjects may receive additional unblinded treatments (i.e. a single FCM 750 mg undiluted slow IV push at 100 mg/minute) if at any time the subject reports worsening of RLS symptoms (an increase > 4 points on the IRLSS compared to the last evaluation captured for that subject) and laboratory criteria are met (ferritin < 300 ng/mL and a TSAT $< 45\%$). No additional treatment will be allowed after the Week 46. A final face-to-face study visit will occur on Week 52. If a clinic visit is not possible, final evaluation will be completed by phone.

The Schedule of Events for Phases I, II and III are presented as Table 1.1 and Table 1.2

Table 1.1 Schedule of Events Treatment Phase I and Treatment Phase II

STUDY VISIT PROCEDURES	SCREENING	Treatment Phase I and Treatment Phase II				
	-14	DAY 0	DAY 7+1	DAY 14+3	DAY 28+3 (PHONE CONTACT)	DAY 42+3
Informed Consent	X					X**
Eligibility	X	X				X
Medical History, including prior iron therapy	X	X				
RLS History	X	X				
D/C oral iron products	X					
Site contact IRT	X					
Physical exam	X					X
Vital Signs	X	X	X			X
Height and Weight without shoes	X					
CHDQ	X					
HTDI	X					
IRLSS	X	X			X	X
HRSQ		X				X
CGI-I						X
PGI-I						X
MOS Sleep Scale		X				X
Hematology	X	X	X	X		X
Iron Indices	X	X	X	X		X
Chemistry	X	X	X	X		X
Vitamin D		X	X	X		X
Erythropoietin		X				X
Trace Element		X				
Urine Pregnancy test	X					
Study Drug		X	X			
Brain MRI	X					X
Concomitant Meds	X	X	X		X	X
Adverse Events		X	X		X	X

** All Subject will be consented to participate in Treatment Phase II prior to any study procedures being completed

Table 1.2 Schedule of Events Long-Term Extension Phase III

STUDY VISIT PROCEDURES	Week 15 Phone Contact	Week 25 Phone Contact	Week 34 Phone Contact	Week 43 Phone Contact	Week 52 EOS
IRLSS	X	X	X	X	X
HRSQ	X	X	X	X	X
MOS / PGI-I					X
Concomitant Meds	X	X	X	X	X
Adverse Events	X	X	X	X	X
Physical Exam / VS	See protocol Section 6.6 for procedures for additional FCM dosing				
Iron Indices / Chemistries / Hematology					X
FCM Dosing					

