- 20. Any other pre-existing laboratory abnormality, medical condition, or disease that, in the opinion of Investigator, may cause the subject to be unsuitable for the study or place the subject at potential risk from being in the study, e.g. a malignancy, uncontrolled hypertension, unstable ischemic heart disease, or uncontrolled diabetes mellitus.
- 21. Subject is unwilling or has conditions that would prohibit them from complying with the study requirements.

RLS Therapy:

Subject should not be receiving treatment for RLS. All treatment for RLS should be discontinued at least 4 weeks prior to screening.

Study Duration – One year:

- Screening Phase: up to 14 days
- Treatment Phase I: 42 days
- Treatment Phase II: 42 days
- Long-term Extension Phase III: up to 46 weeks

Number of Subjects / Sample Size:

Enrollment is planned for completion (reaching Day 42 final assessment) of 70 randomized subjects (35 per treatment group). Based on Study 1VIT05009 in RLS subjects without IDA, approximately 50% of subjects in the FCM group and 15% of subjects in the placebo group are anticipated to have much or very much improvement on the CGI-I.³⁵ The proposed sample size provides >85% power to detect this difference with the chi-square test. The mean treatment difference and standard deviation of 5.0 (7.3) is estimated for change from Baseline to Day 42 for IRLSS score. The proposed sample size provides >80% power to detect this difference with the unpaired t-test.

Statistical Analyses:

The percentage responding to treatment will be evaluated for each drug condition in Treatment Phase I to determine the treatment difference at Day 42. This will be calculated from the IRLSS as change from Baseline and for the CGI-I with response determined as much or very much improved (scores of 1 or 2). All scores greater than 2 on the CGI-I are considered to indicate no significant response. For Phase II, the proportion of treatment non-responders in Phase I who respond to FCM in Phase II will be estimated and the IRLSS score, CGI-I, and PGI-I will be summarized at Day 42. The duration of treatment over the follow-up to end of study will be described as the percentage of responders and the IRLSS score change from Baseline at each time point. Time to first FCM dose after start of Phase III will be estimated with Kaplan-Meier methodology.

CONTACT PERSON FOR THE STUDY

For study related questions please contact:

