2. STATISTICAL METHODS

2.1 GENERAL CONSIDERATIONS

Analysis datasets will be produced according to CDISC standards. All study-collected data will be summarized in tables or graphs. Listing will be produced when appropriate and all ICH-required listings will be produced. In general, continuous variables will be summarized by number of subjects, mean, standard deviation (SD), median, minimum, and maximum values. Categorical variables will be summarized by number and percentage of subjects in each category.

In general, summary tables will present data by treatment group (for Phase I) and treatment phase.

Baseline definitions:

- Phase I: baseline (other than iron index) is the last non-missing value prior to receiving randomized study medication.
- Phase II: phase II baseline (other than iron index) is the last non-missing value prior to receiving unblinded FCM in Phase II.
- Phase I and Phase II: baseline for iron index measured by MRI is measured in screening.
- Phase III: phase III baseline is defined as Day 0 of Phase I for responders in Phase I and Day 0 of Phase II for responders in Phase II.

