6.1.3 Phase III: Time from initial FCM treatment to further FCM treatment

Time (weeks) from the initial FCM treatment to further FCM treatment received in Phase III will be calculated as the integer of $(\text{date of the further FCM treatment in Phase III} - \text{date of the initial FCM treatment}) / 7 + 1$. The time duration will be summarized via descriptive statistics including number of subjects, median, minimum (min) and maximum (max). Initial treatment is defined as Day 0 of Phase I for responders in Phase I and Day 0 of Phase II for responders in Phase II. At any time before week 46 subject could receive a single dose of unblinded FCM treatment (i.e. the further FCM treatment) if RLS symptom is worsened.

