6.2.10 Phase III: Change in IRLSS total score from baseline to each visit

The actual value of IRLSS total score on baseline and each scheduled visit (i.e. Weeks 15, 25, 34, 43 and 52 via phone contact), and change from baseline to each scheduled visit will be summarized via descriptive statistics.

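### The SAP counts Phase III weeks from Phase I Day 0 but starts Phase II responders' baseline 6 to 7 weeks later, so the by-visit IRLSS table mixes times since baseline and the 46-week extension does not fit

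*SAP*

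**What the plan says.** SAP 1.3.1 takes responders from Phase I and from Phase II into "this 46-week long-term extension phase of the study" and assesses them at "Weeks 15, 25, 34, 43 and 52 (final follow-up visit) from treatment Phase I Day 0".

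Two other SAP sections use a different origin for Phase II responders. Under SAP 2.1, "phase III baseline is defined as Day 0 of Phase I for responders in Phase I and Day 0 of Phase II" for those who respond in that phase. Under SAP 6.1.3, "Initial treatment is defined as Day 0 of Phase I for responders in Phase I and Day 0 of Phase II" for the same subjects. SAP 1.3.1 fixes the distance between the two origins: "Day 0 of treatment Phase II will occur within 7 days of the completing Treatment Phase I Day 42 visit".

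SAP 6.2.10 summarises IRLSS values and change from baseline at each scheduled visit, listed as "Weeks 15, 25, 34, 43 and 52 via phone contact". It names no split by phase of response. SAP 2.1 splits tables by treatment group for Phase I only, and SAP 2.3 builds no visit windows.

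The protocol is less definite:

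- The Synopsis and section 3.2 label the qualifying Day 42 visit Week 6 for responders from either phase.
- The Synopsis and section 6.5 put Week 52 about 365 days after the initial Day 0 treatment, without naming the phase.
- The Synopsis defines initial treatment as Phase II Day 0 for Phase II responders.
- Under Study Duration, the Synopsis gives one year overall and "Long-term Extension Phase III: up to 46 weeks".

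**The concern.** The SAP runs two clocks. The visit label counts from Phase I Day 0, while the change score counts from the subject's own Day 0. They agree for Phase I responders and differ by a whole treatment phase for Phase II responders. Nothing in SAP 2.1, 2.3 or 6.2.10 realigns or separates the groups, so one row of the table would hold change scores taken at clearly different times since baseline.

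The primary objective of Phase III is duration of effect, and SAP section 6 plans no Phase III testing. The by-visit table is therefore the result itself, and its time labels need to be right. The two clocks also make the stated length of the extension impossible for one of the two groups that enter it.

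**Working it through.** **Inputs.** Phase I Day 42 visit: day 42, with an allowance of +3 days (SAP Table 1.1). Gap to Phase II Day 0: 0 to 7 days (SAP 1.3.1). Visits: Weeks 15, 25, 34, 43 and 52 from Phase I Day 0 (SAP 1.3.1). Last permitted Phase III dose: Week 46 (SAP 1.3.1). Study week below means weeks from Phase I Day 0.

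**The plan's own figure.** For a Phase I responder the extension runs from Day 42 to Week 52: 52 - 42/7 = 52 - 6 = 46 weeks. The stated 46 weeks is reproduced.

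**Offset between the clocks.** Offset = (42 + gap)/7.

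- Gap 0 days: 42/7 = 6.0 weeks
- Gap 7 days: 49/7 = 7.0 weeks
- Gap 7 days with the +3 days used: 52/7 = 7.4 weeks

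**Time since own baseline at each nominal visit.** Nominal week minus offset, for Phase II responders:

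| Nominal week | Phase I responders | Phase II responders | With the +3 days |
|---|---|---|---|
| 15 | 15 | 8-9 | 7.6 |
| 25 | 25 | 18-19 | 17.6 |
| 34 | 34 | 27-28 | 26.6 |
| 43 | 43 | 36-37 | 35.6 |
| 52 | 52 | 45-46 | 44.6 |

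The offset is 40-47% of the nominal time at Week 15 (6/15 to 7/15) and 12-13% at Week 52 (6/52 to 7/52).

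**Extension length for Phase II responders, SAP clock.** Phase II Day 42 falls at study week 6 + 6 = 12 to 7 + 6 = 13. To Week 52 that leaves 52 - 13 = 39 to 52 - 12 = 40 weeks (38.6 with the +3 days on the Phase I visit), not 46. Week 15 comes 15 - 13 = 2 to 15 - 12 = 3 weeks after their qualifying visit, against 15 - 6 = 9 weeks for Phase I responders.

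**Week 46 cut-off.** On the same clock it falls 46 - 7 = 39 to 46 - 6 = 40 weeks after Phase II Day 0, against 46 weeks after Phase I Day 0. These are elapsed weeks, before the +1 in the SAP 6.1.3 formula.

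**The other reading: weeks from each subject's own Day 0.** The offset at every visit is then zero and the extension is 52 - 6 = 46 weeks for everyone. Phase II responders finish at study week 52 + 6 = 58 to 52 + 7 = 59 (59.4 with the +3 days). The Synopsis gives the study duration as one year.

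**The case against.** The strongest objection is that the mixing depends on the SAP's clock being the one used to schedule visits. SAP 1.3.1 is a design summary, and the protocol passages fit a count from each subject's own Day 0. The SAP also cites a protocol dated 4 September 2019, while the protocol supplied carries April 2016 dates, so the governing visit wording may not be in view. This stands as a limit on certainty. It does not remove the conflict, because the own-Day-0 reading contradicts the SAP's explicit origin and the one-year duration. SAP section 9 lists no change of time origin.

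The protocol's Study Duration entry says up to 46 weeks, which allows a shorter extension. That is fair for that entry, but SAP 1.3.1 and protocol sections 3.2 and 6.5 give 46 weeks without that qualifier.

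Pooling in 6.2.10 is inferred from the general table layout; the section does not state it. The effect is also narrow. Phase III is descriptive, the study ended early, and the time to further FCM in SAP 6.1.3 already starts from each subject's own Day 0.

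A reader might infer that pooling makes the effect look better sustained than it is, since Phase II responders are seen earlier than the label says. The documents do not support that. They give no curve of IRLSS against time since treatment, re-dosing during Phase III would interrupt a simple decline, and the relative offset is smallest at the later visits. Nor is the label a clean count since FCM. Phase II responders first randomized to FCM had a course at Phase I Day 0, and Phase I placebo responders had none at theirs.

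A reader might also try to estimate the share of Phase III made up of Phase II responders. The planning rates of 50% and 15% are CGI-I rates rather than responder rates, no Phase II response rate is given, and the numbers at early termination are not stated. No usable share follows.

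**Conclusion.** The point holds for the SAP as written and is minor. Phase II responders are 6 to 7 weeks closer to baseline than the visit label says (up to about 7.4), and their extension to Week 52 is 39-40 weeks rather than 46. This assumes that visits follow SAP 1.3.1 and that 6.2.10 follows the general layout without a split. If visits instead follow each subject's own Day 0, the table is aligned, but the SAP wording is wrong and the one-year duration is exceeded by Phase II responders. The passages conflict on either reading.

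The consequence is confined to descriptive Phase III by-visit summaries. No test, power or sample-size figure depends on it, and the direction of any bias is not established. The origin of the time-to-further-FCM measure is sound, though on the SAP's clock its longest observable time differs by group (46 against 39-40 weeks).

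**What to change.** In SAP 6.2.10, tabulate IRLSS values and changes separately by phase of response. For any pooled display, use actual weeks since initial treatment, (visit date - own Day 0)/7, as the time axis.

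Reconcile the protocol and SAP so that both state which Day 0 is the origin for Weeks 15 to 52, for the Week 46 cut-off and for the 46 weeks, and how this fits the one-year duration. Which origin applies is for the sponsor to settle.

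The cost is a few lines of SAP wording and one by-group split. No new data are needed, since SAP 6.1.3 already uses the initial-treatment date. Cells become smaller. The split corrects timing only: Phase I placebo responders and Phase I FCM responders would still share a stratum.

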1.3.2 Randomization and Blinding

On Day 0 of **treatment Phase I**, all eligible subjects will be randomized via IRT system in a 1:1 ratio to receive a blinded dose of either FCM 750 mg undiluted slow IV push at 100 mg/minute or a Placebo (15 ml of Normal Saline) IV push at 2 ml/minute.

Other than designated randomization personnel, all subjects, investigators, and study conduct personnel are blinded to study drug assignment. The blinded investigators are also blinded to the IRLSS total score and PGI-I score for each subject after randomization. All study personnel will be blinded to the post treatment iron indices and phosphorous (after randomization) throughout the study.

1.3.3 Sample Size and Statistical Power Considerations

Enrollment was planned for 70 randomized subjects (35 per treatment group in Phase I). Based on Study 1VIT05009 in patients without IDA, approximately 50% of patients in the FCM group and 15% of patients in the placebo group are anticipated to have much or very much improvement on the CGI-I. The proposed sample size provides >85% power to detect this difference with the chi-square test. The mean treatment difference (and standard deviation) for change from baseline to Day 42 for IRLSS is anticipated to be 5.0 (7.3). The proposed sample size provides >80% power to detect this difference with a two-sided t-test with alpha=0.05.

2. STATISTICAL METHODS

2.1 GENERAL CONSIDERATIONS

Analysis datasets will be produced according to CDISC standards. All study-collected data will be summarized in tables or graphs. Listing will be produced when appropriate and all ICH-required listings will be produced. In general, continuous variables will be summarized by number of subjects, mean, standard deviation (SD), median, minimum, and maximum values. Categorical variables will be summarized by number and percentage of subjects in each category.

In general, summary tables will present data by treatment group (for Phase I) and treatment phase.

Baseline definitions:

- Phase I: baseline (other than iron index) is the last non-missing value prior to receiving randomized study medication.
- Phase II: phase II baseline (other than iron index) is the last non-missing value prior to receiving unblinded FCM in Phase II.
- Phase I and Phase II: baseline for iron index measured by MRI is measured in screening.
- Phase III: phase III baseline is defined as Day 0 of Phase I for responders in Phase I and Day 0 of Phase II for responders in Phase II.

